6.0 Procedures Involved

The current study involving human subjects consists of a Randomized Controlled Trial to test the feasibility, effectiveness, and implementation of the TASC intervention as compared to a treatment as usual group. A total of up to 80 adolescents with moderate or severe persistent asthma between the ages of 12-18 years will be randomized to TASC (n=35) or treatment as usual (n = 35). After adolescent participants have met inclusion criteria, completed baseline assessments, and have been enrolled in the feasibility RCT, they will be randomized to either TASC or Treatment As Usual (TAU). The statistician will make the randomization schedule and the principle investigator will maintain randomization schedule. Outcomes measures (adherence and disease severity) will be assessed at baseline, monthly during active treatment, and at post-treatment, with the primary endpoint being post-treatment.

Participants will be enrolled in the study for a duration of six months. First, participants will complete baseline questionnaires related to demographic, and clinical predictors of adherence and asthma. Participants will be randomized following completion of baseline measures. A smart phone prepared by the CCHMC IT team with a data plan will be provided to participants who do not have their own cellphone. Propeller or FindAir adherence caps will also be provided to all participants and utilized for 2 months without

PROTOCOL TITLE: Using Technology- Assisted Stepped Care Intervention to Improve Adherence in Adolescents with Asthma

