12.0 Local Number of Subjects

Up to 80 adolescents will be enrolled in the current study.

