For H3 acceptability, descriptive statistics of participant-reported and provider-reported satisfaction with intervention structure, length, convenience, and perceived impact on outcomes will be assessed⁸⁶. For usability, the statistical test of choice will be one-sample t-test tested at the nominal $\alpha_{2\text{-tailed}} = 0.05$ level. Usability will be evaluated using the SUS and a comparison score of 71 indicating good usability.⁸⁷ For reach, representativeness of the sample and enrollment rate of underserved individuals will be assessed. For sustainability, facilitators and barriers to delivering the intervention will be assessed.

Exploratory Aim: Examine clinical, demographic, and behavioral predictors of attendance, acceptance, and improvement in medication adherence and health within each intervention step.

Mediation and moderation of treatment effects will be examined using strategies outlined by Barron and Kenny⁸⁸, Holmbeck and colleagues^{89,90} using candidate covariates believed to be in the causal chain, including but not limited to, demographic characteristics, asthma symptoms, clinical presentation, treatment outcome expectancy (CEQ), and externalizing and internalizing problems (BASC).

A total of 60 participants will be needed for Hypothesis 1 analyses. Monte Carlo simulations in Mplus (version 8.1) were conducted to estimate statistical power assuming: 1) baseline adherence, asthma exacerbations, and race/ethnicity could explain between ($R^2 = 0.20-0.40$) 20%-40% of response variable noise variance, 2) participant attrition could range between 0%-20%, 3) alpha = .05, and 4) pre-post correlations similar to those reported in both the intervention literature and observed in our lab. The power analysis question involved identifying the smallest d effect size difference under these assumptions. Assuming proper handling of missing data, results showed power will be ≥ 0.80 for $d \geq 0.72$. Effect sizes larger than the one proposed have been documented in published studies^{12,91}, however, if statistical significance is not achieved, effect size estimates would inform design and power considerations for subsequent efficacy studies to further evaluate the TASC intervention. Up to 80 participants will be recruited to account for attrition.

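### The arm sizes in Section 6.0 (35 and 35) sum to 70, up to 10 short of the total of up to 80 in the same sentence

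*Combined protocol and SAP*

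**What the plan says.** Section 6.0 (Procedures Involved) opens its account of randomisation with the total: "A total of up to 80 adolescents with moderate or severe persistent asthma". The same sentence then gives the split: "will be randomized to TASC (n=35) or treatment as usual (n = 35". The sentence after it sends everyone who has met the criteria, finished baseline assessment and been enrolled to one of the two arms. Responsibility for the list follows: "The statistician will make the randomization schedule and the principle investigator will maintain randomization schedule".

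The total appears in three other places. The Section 1.0 summary table gives a sample size of 80. Section 12.0 says "Up to 80 adolescents will be enrolled in the current study". Section 17.0, which holds the statistical text, says "Up to 80 participants will be recruited to account for attrition".

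No other section gives a number per arm, and none states an allocation ratio, a blocking scheme or a third arm. The revision history lists, as revision 9 (8/16/2023), a change of sample size from 70 to 80.

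**The concern.** Section 6.0 is the only place that says how participants are divided between TASC and treatment as usual. Its arm sizes do not add up to the total in their own sentence. They are also the only basis in the document for inferring equal allocation.

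The matter at stake is practical. A statistician preparing or extending the randomisation list, or anyone checking later whether the trial enrolled to plan, would take the target per arm from this sentence. Read one way it gives 70 and read the other way 80. The document should give one answer.

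**Working it through.** **Inputs**

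- Total to be randomised: up to 80 (Section 6.0).
- TASC arm: 35 (Section 6.0, same sentence).
- Treatment-as-usual arm: 35 (Section 6.0, same sentence).
- Total elsewhere: 80 (Section 1.0), up to 80 enrolled (Section 12.0), up to 80 recruited (Section 17.0).

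**Step 1: try to reproduce the stated total from the arms.**

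Sum of arms = 35 + 35 = 70. The stated total is up to 80, so it is not reproduced.

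**Step 2: size of the gap.**

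80 − 70 = 10, and 10 / 80 = 12.5%. Because 80 is an upper limit, the gap is at most 10. If 70 or fewer are enrolled, it does not arise.

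**Step 3: decide which figure is out of line.**

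| Place | Figure |
|---|---|
| Section 1.0 | 80 |
| Section 6.0, total | up to 80 |
| Section 12.0 | up to 80 |
| Section 17.0 | up to 80 |
| Section 6.0, arms | 35 + 35 = 70 |

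Four statements agree on 80. The arm sizes stand alone.

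**Step 4: look for a reading that reconciles them.**

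- *A third arm, or a group that is not randomised.* None is described.
- *80 recruited, of whom 70 are randomised.* The sentence in Section 6.0 attaches the 80 to randomisation itself. The next sentence randomises participants once they are enrolled, and no stage of loss is described in between.
- *An allowance for attrition.* Section 17.0 gives attrition as the reason for recruiting up to 80. That explains why the total is larger, but it does not divide the larger total between the arms.

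**Step 5: likely origin.**

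70 is exactly the sample size that revision 9 replaced, and 35 is half of it. The simplest explanation is that the total was edited and the two arm sizes were not. This is an inference. The finding does not depend on it, because both figures stand in one sentence of the current text.

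**Step 6: arm sizes that agree with the total.**

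With equal allocation, 80 / 2 = 40 per arm. Equal allocation is implied by 35:35 but not stated.

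**The case against.** The strongest reply is that this is a missed edit with no demonstrated consequence. Most of that stands. Arms that sum to 70 do not exceed a ceiling of 80, so the sentence is inconsistent as a target rather than logically impossible. Every enrolled participant is to be randomised to TASC or treatment as usual, whatever the printed counts. All statements of the total say 80, and nothing shows that enrolment or the list stops at 70.

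Two stronger readings are tempting, and the document supports neither.

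First, a reader might infer that 10 participants have no arm. The sentence after the arm sizes rules this out. What fails to add up is the planned count.

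Second, a reader might infer that the trial is short of power. Section 17.0 says "A total of 60 participants will be needed for Hypothesis 1 analyses" and allows that "participant attrition could range between 0%-20" per cent. Starting from 70, a 20% loss leaves 70 × 0.80 = 56, below 60. That requires three things together: the 35/35 split is followed in place of the stated 80, the 60 means participants analysed, and attrition exceeds 10 / 70 = 14.3%. The stated total of 80 leaves 80 × 0.80 = 64 at the same loss. Attrition is also listed among the inputs to the simulation, and the plan adds "The power analysis question involved identifying the smallest d effect size difference under these assumptions". The 60 may therefore already allow for attrition, in which case the worst case planned for is 60 × 0.80 = 48 analysed, and 56 exceeds it. On neither reading does the 35/35 figure undermine the power statement, which is built on 60.

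What the reply does not remove is the inconsistency itself. It lies within the current text, so it is not merely a difference from the revision history, and it sits in the only text that sets out allocation.

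**Conclusion.** The planned count per arm in Section 6.0 is wrong as written. The arms sum to 70 against a total of up to 80, a gap of up to 10 participants or 12.5% of the total. This rests on addition alone and needs no statistical assumption.

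Taking the arm sizes, rather than the total, as the figure to correct rests on the agreement of the four statements of 80. The figure of about 40 per arm rests on the further assumption that allocation is 1:1. That the arm sizes were left over from the earlier sample size is probable but not shown.

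The point should be corrected because it concerns the sample size in the operative allocation text. It gives no ground for changing the sample size, the stated effect size or the power statement.

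**What to change.** In Section 6.0, restate the two arm sizes so that they agree with the total of up to 80: about 40 in TASC and about 40 in treatment as usual, if allocation is 1:1. The word about is preferable to a fixed cap, because no blocking is described and simple randomisation of 80 need not give exactly 40 and 40. Stating the allocation ratio in the same edit would remove the need to infer it.

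As a precaution, confirm that the randomisation schedule covers all 80. The schedule is not part of the document, and nothing suggests that it is deficient.

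The cost is a one-line text correction and one check of an existing list.

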feedback to obtain baseline adherence. If the participant did not bring their inhalers to the appointment, a coordinator will follow up with the patient to ensure that the Propeller or FindAir sensors are properly attached to the patients' inhalers. In addition, all participants receive a mobile spirometer (Spirobank Smart) to track their lung function throughout the study. The spirometer connects to an app (Propeller or FindAir) via Bluetooth. This app allows the participant to perform pulmonary function tests (PFTs) and view the results of these tests, such as their forced expiratory volume (FEV1) as well as other lung function parameters. Participants will be asked to use the spirometer at least once a month when completing study visits over the phone with a study team member. Following the baseline visit, a 8 week run-in phase will be completed to assess baseline adherence using electronic inhaler monitoring. After 4 weeks in baseline, the coordinator will call the participants in TASC and TAU for their first monthly phone call. After obtaining 8 weeks of baseline adherence data, the coordinator will call the participants in TASC and TAU for their second monthly phone call. The coordinator will calculate baseline adherence and obtain data for the Composite Asthma Severity Index (CASI) and the Asthma Control Test (ACT) for TASC and TAU participants. For TASC participants only, the coordinator will introduce Step 1 of the intervention for all participants. Adherence checks will continue to occur every four weeks for the duration of the study for all participants and adherence <68% will prompt movement from one level of treatment to the next for TASC participants only. The study coordinator will calculate the participant's adherence percentage prior to the monthly telephone call. During the call, the coordinator will tell the participant if they will get moved up to the next step and explain what they will be doing during that step. TASC participants may remain at a treatment level for more than four weeks and may complete 1, 2, or 3 interventions steps during the 5 month study depending on the adolescent's adherence.

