13.0 Recruitment Methods

Adolescents will be recruited through the CCHMC Asthma Center, which conducts 4500 patient visits each year. Eligible adolescents will be identified through electronic medical records and approached during outpatient medical visits. Adolescents with a history of nonadherence per physician report will be targeted. Study staff will meet with interested adolescents and parents to confirm eligibility and obtain written consent/assent.

Adolescents may also be recruited via telephone. For the patients study staff plan to recruit via phone, a recruitment letter will be mailed or emailed to eligible families with upcoming pulmonary appointments, which will describe the study briefly and include an “opt out” phone number to call if they do not wish to be contacted about the study. Two weeks after sending the letters, study staff will call potential participants to discuss the study more thoroughly. Reasons for decline and sample composition will be tracked throughout the study to ensure accurate representation and to examine the reach of the intervention based on the enrollment rate of high-risk or underserved individuals.

Participants will be compensated for their participation in the amount of \$50 for the baseline assessment, \$20 at the end of month 1, \$20 at the end of month 2, \$25 at the end of month 3, \$30 at the end of month 4, \$40 at the end of month 5, \$75 at the end of the study. In addition, participants will be paid \$10 a week for syncing their Propeller or FindAir caps in conjunction with the Step 2 texting intervention, allowing the interventionists to obtain the data needed to complete the intervention. Participants who qualify for behavioral intervention sessions will be paid \$15 per session for up to four sessions. In the event that a study phone is not returned, we will attempt via phone and email to reach the family and set up a way to retrieve it in person or via mail. Given the high cost of the phones, if, after several months it is still not returned, we may offer an incentive of \$50 for the safe return of the working mobile device, no questions asked.

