14.0 Withdrawal of Subjects

Participants may withdraw from the study at any time and will be informed of this right verbally and in writing during the consent process. The principle investigator may remove participants from the study for abuse of CCHMC device privileges (see cell phone contract).

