15.0 Risks to Subjects

This is a minimal risk study. All behavioral assessments and questionnaires have been used in research without any reported negative effects; rarely, participants experience mild temporary distress related to completion of behavioral measures. The adherence trackers (Propeller Health or FindAir) that will be provided to participants are registered with the FDA as a Class 1 Medical Device and therefore only pose minimal risk. Families also might be slightly inconvenienced by participating over a short period of time.

Several precautions will be taken to minimize the risk, discomforts, and inconveniences associated with this protocol. First, the PI is a licensed clinical psychologist and will oversee all study components. Thus, in the unlikely event of psychological distress resulting from questionnaires or assessment components, appropriate treatment and/or referrals can be easily made. All assessment components will be completed online or in conjunction with a pulmonary clinic appointment to lessen the burden of time and travel for families.

Knowledge gained in this study has the potential to improve treatment of pediatric asthma by enhancing disease management skills that, consequently, would improve treatment outcome in this population. The minimal risk posed to participants by this study is acceptable given that the knowledge that reasonably may be expected to result is substantial to the overall treatment of these patients and their families.

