18.0 Provisions to Monitor the Data to Ensure the Safety of Subjects

This study involves minimal risk to participants. Study personnel at CCHMC will monitor data collection, progress through treatment, any technical difficulties that may arise, adverse events, and completion of study procedures. Any adverse events (i.e., breach of confidentiality or events that are unexpected and related to the intervention) will be reported to the IRB within 48 hours. Participation will be discontinued at parent or patient request or if the investigators deem that it is in the best interest of the patient's health. The study team will provide referrals as appropriate for treatment needs resulting from any adverse events. The IRB requires yearly renewal of study protocols, which provides additional monitoring of participant safety. All other adverse events that happen in the course of the study procedures as well as minor deviations from protocol will be reported in table form at the next yearly continuing IRB review. The PI will review study data with her primary mentor at weekly meetings to ensure safety compliance and proper reporting to the IRB. In addition, the PI will have quarterly meetings with her mentorship team to monitor the progress of the study, the integrity of the treatment, discuss the need for any protocol refinements, and conduct regular safety monitoring checks of adverse

PROTOCOL TITLE: Using Technology- Assisted Stepped Care Intervention to Improve Adherence in Adolescents with Asthma

events. The PI will report any significant study related or unanticipated adverse events to not only the IRB, but also to the study sponsor based upon institutional and sponsor guidelines. Given that this pilot study is using evidence-based intervention, we believe that monitoring at the level of the PI, her mentors and research team, with oversight from the IRB and study sponsor is sufficient.

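### The principal investigator keeps the pre-made randomisation schedule, and the plan states no safeguard that conceals upcoming assignments

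*Combined protocol and SAP*

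**What the plan says.** On custody of the list, Section 6.0 (Procedures Involved) says: "The statistician will make the randomization schedule and the principle investigator will maintain randomization schedule". On the custodian's role, Section 15.0 (Risks to Subjects) says: "First, the PI is a licensed clinical psychologist and will oversee all study components".

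On entry to the trial, Section 13.0 (Recruitment Methods) says: "Study staff will meet with interested adolescents and parents to confirm eligibility and obtain written consent/assent". It also says: "Adolescents with a history of nonadherence per physician report will be targeted". Section 10.0 repeats that targeting in its introduction, but the list of inclusion criteria does not contain it. Recruitment is in clinic or by telephone.

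On timing, Section 6.0 says: "Participants will be randomized following completion of baseline measures". On who knows the arm afterwards, the same section has one coordinator telephoning both arms and adds: "For TASC participants only, the coordinator will introduce Step 1 of the intervention for all participants". No blinding of investigator, staff or assessors is described.

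The document mentions no sealed envelopes, central or system-based release, independent custodian, or rule on who may see the schedule. It gives no block size or stratification.

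**The concern.** A schedule made in advance is a list of future assignments. Whoever keeps it can read the next one unless something prevents that, and here the keeper leads the recruiting team.

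Recruitment leaves room for judgement. A history of nonadherence is a target and not a criterion, so which family to approach, and when, is partly discretionary. That judgement also bears on the primary outcome, adherence. If the next arm were known, more motivated adolescents could be brought forward when TASC is next and others when usual care is next, without anyone intending it.

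Such selection would bias the adherence comparison and the CASI comparison. Section 17.0 plans ANCOVA, and its power paragraph names baseline adherence, exacerbations and race/ethnicity as explanatory variables. Motivation and family support are not among them. With 60 to 80 participants, steering could not be ruled out afterwards from baseline tables. Section 17.0 also intends the effect estimates to inform later efficacy studies, so a bias would carry forward.

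**Working it through.** **1. The plan's own figure, for scale.** Section 17.0 states 60 participants, attrition of 0% to 20%, R² of 0.20 to 0.40, alpha .05, and power of at least 0.80 for d of 0.72 or more. The least favourable corner is 60 × 0.80 = 48 analysed with R² = 0.20. The noncentrality is 0.72 × √48 / 2 / √0.80 = 2.79. Two-sided power is 0.796 by the normal approximation, or 0.778 by the noncentral t with three covariates. The stated figure is thus approximately reproduced and is not in dispute. The sidedness of alpha for Hypothesis 1 is not stated; two-sided is assumed here.

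**2. How predictable the next assignment is.**
- For a person who can read the list: 100%.
- Under concealed simple randomisation with equal allocation: 50%.
- In an open trial with known blocks of size 2b, the best guess is right with probability [b + (4^b / C(2b, b) − 1) / 2] / (2b). For blocks of 4: (2 + 0.833) / 4 = 71%. For blocks of 6: (3 + 1.1) / 6 = 68%.

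The plan does not mention blocks. This comparison only shows why block sizes, if used, should be withheld too.

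**3. What steering would do, under assumed values.** The document gives no rate of steering. Suppose that in a fraction f of enrolments the better of two candidates is taken for TASC and the worse of two for usual care, and that perceived prognosis correlates r with the outcome. The expected maximum of two standard normals is 1/√π = 0.564, so

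bias in SD = 2 × 0.564 × r × f.

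Inputs: 80 × 0.80 = 64 analysed, R² = 0.20, three covariates, 59 degrees of freedom, critical t = 2.00. The noncentrality is bias × √64 / 2 / √0.80. The true treatment effect is set to zero.

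| r | f | Bias (SD) | Noncentrality | Type I error | Type I error if covariates absorb 20% of the shift |
|---|---|---|---|---|---|
| any | 0 | 0 | 0 | 5.0% | 5.0% |
| 0.3 | 0.10 | 0.03 | 0.15 | 5.3% | 5.2% |
| 0.3 | 0.25 | 0.08 | 0.38 | 6.6% | 6.0% |
| 0.3 | 0.50 | 0.17 | 0.76 | 11.6% | 9.2% |
| 0.5 | 0.50 | 0.28 | 1.26 | 23.7% | 16.8% |

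The last column multiplies the bias by 0.80 and keeps the rest. With R² = 0.40 and 40% of the shift absorbed, the last three rows become 5.8%, 8.1% and 13.8%.

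**4. Does the order of steps close the gap?** Section 6.0 places randomisation after eligibility, baseline assessment and enrolment. That sequence prevents selection only if the next assignment is hidden until it is complete. Set beside the custody sentence, nothing in the document secures that.

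**The case against.** The strongest reply is that maintaining a schedule is not the same as reading it. The word could cover custody of a sealed or logged list, in which case the sentence is harmless. Study staff, not the investigator by name, approach families and obtain consent, and no text gives those staff access to the list. The oversight sentence in Section 15.0 comes from a paragraph on minimising risk and distress. All of this stands. A reader might infer that recruiters know the upcoming assignments; the document does not say so. What it supports is access for the head of the team, without a stated safeguard.

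The sequence of steps also counts. Telephone recruits receive a letter, are called two weeks later and may decline, so the family who will fill the next slot is uncertain when approached. That makes steering harder. It does not exclude it, because the timing of approach, consent and baseline completion remains in the team's hands.

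One could call this a missing detail. In part it is, but the plan does state who keeps the list, and a better custodian is already named in the same sentence.

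The illustrative figures are open to challenge. Nothing in the document supports any value of r or f, and f = 0.50 means that half of all enrolments are steered. The upper rows of the range should not be read as an expected size.

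Finally, this is a feasibility trial of preliminary efficacy. That moderates the stakes, but Hypothesis 1 is still a between-arm comparison powered at alpha .05.

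**Conclusion.** The point holds in a limited form. The investigator who oversees the trial has custody of the pre-made schedule, and no concealment measure is stated. Upcoming assignments are accessible inside the team that recruits, and adjustment for measured covariates would only partly correct any resulting imbalance.

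The size is unknown. The range of 6.6% to 23.7%, or 6.0% to 16.8% with one fifth of the shift absorbed, rests wholly on assumed values of r and f, equal arms, 64 analysed and R² = 0.20. With no steering the error rate stays at 5%. The assumed shifts of 0.08 to 0.28 SD compare with a planned detectable effect of 0.72.

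A reader might also connect custody of the list with the power in Section 14.0: "The principle investigator may remove participants from the study for abuse of CCHMC device privileges". That does not belong to this point. It concerns participants whose arm is already known, which is a question of attrition in any open trial whoever holds the list, and the change below would not affect it. Nor does the document support any suggestion that an assignment has been misused.

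**What to change.** Replace the custody sentence in Section 6.0 with:

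> The statistician will generate the randomisation schedule and hold it, or load it into the REDCap randomisation function. Each assignment is released one participant at a time, only after eligibility, consent and baseline completion are recorded for that participant. The principal investigator, coordinators and interventionists have no access to the schedule or, if blocks are used, to the block sizes.

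Apply this to all remaining participants, and state in the trial report who had access to the list before the change. The protocol is at version 10.0 of August 2023, with revisions dating from 2019, so enrolment may be well advanced (an inference). The change would then protect only the assignments still to come, and disclosure lets readers judge the rest.

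The cost is one amended sentence and a small set-up task in REDCap, which the trial already uses for consent and questionnaires, or none of the set-up if the statistician keeps the list. Sample size, alpha, analysis and participant procedures are unchanged. The small downside is that each assignment must be requested from the system or the statistician.
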